5.5 Sample size considerations

The required sample size for the test is based on the following assumptions:

The ratio of AA to CRC in general risk population is 10:1;

Among the population aged 30 - 75, approximately 30 out of every 10,000 people are patients with CRC and 300 out of every 10,000 people are patients with AA;

The sensitivity and specificity of fecal-based miR-92a detection for CRC are 90% and 90%, respectively. The sensitivity and specificity of fecal-based miR-92a detection for AA are 80% and 90%, respectively;

The sample dropout rate is 5%.

According to the Buderer formula [13], the required sample size is estimated as follows:

Step1: Specifications

SN: sensitivity; SP: specificity; 1- α : confidence level; $Z_{1-\alpha/2}$: standard normal deviation (when $\alpha = 0.05$, $Z_{1-\alpha/2} = 1.96$); W: allowable error, set to 0.09 here; Prevalence: prevalence rate, which is the ratio of positive cases in all samples. We set the prevalence rate for CRC to be 0.3% and the prevalence rate for AA to be 3%.

Step2: Calculate the number with disease, TP + FN

TP + FN =
$$Z_{1-\alpha/2}^2 \frac{SN(1-SN)}{W^2}$$

Step3: Calculate the sample size required for sensitivity, N₁

$$N_1 = \frac{TP + FN}{P}$$

For CRC, $N_1 = 14,228$; for AA, $N_1' = 2,529$

Step4: Calculate the number without disease

$$FP + TN = Z_{1-\alpha/2}^{2} \frac{SP(1 - SP)}{W^{2}}$$

Step5: Calculate the sample size required for specificity, N2

$$N_2 = \frac{FP + TN}{1 - P}$$

For CRC, $N_2 = 43$; for AA, $N_2' = 78$

Step6: Select the final sample size, N

$$N = 14,228$$

In summary, considering a 5% dropout rate, the required sample size is 14,975. To ensure sufficient sample size after excluding unqualified samples, 15,586 individuals were ultimately included in this study.

6. Research program design and processes

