6.6 Follow-up management

According to the protocol design and workflow, the study will be conducted in subjects who are positive for fecal-based miR-92a and/or FIT, and a random sample of subjects who are negative for tests will be randomly selected for colonoscopy, and subjects will be followed up until completion of colonoscopy. Individuals who have undergone

screening and require confirmatory testing should promptly schedule a colonoscopy and engage in health education sessions without delay.

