7.4 Statistical methods

A variety of categorical data analysis methods will be used to analyze the results from the miR-92a, FIT and FIT + miR-92a results. Binomial proportions and exact 95% CI summarize sensitivity and specificity across categories. According to the study design, FIT and miR-92a from the same subjects were considered as a paired design, and the exact McNemar's test was used to compare the differences of DR, PR, Se and Sp between these two groups. Given the susceptibility of PPV to confounding factors like prevalence and subject characteristics, the GEE (Generalized Estimating Equations), which is based on McNemar's test, was utilized to compare the differences in PPV between the two groups.

8. Ethical issues

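### The 0.09 allowable error for CRC sensitivity in section 5.5 requires verified disease status in every evaluable subject; the colonoscopy scheme verifies only a fraction

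*Protocol*

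**What the plan says.** Section 5.5 uses the Buderer formula with z = 1.96 and an error term described as "W: allowable error, set to 0.09 here". Its performance assumptions are "The sensitivity and specificity of fecal-based miR-92a detection for CRC are 90% and 90%, respectively" and "The sensitivity and specificity of fecal-based miR-92a detection for AA are 80% and 90%, respectively". Prevalence is set at 0.3% for CRC and 3% for AA. CRC sensitivity gives the largest requirement, 14,228, and so fixes the final number. The only loss quantified is dropout: "In summary, considering a 5% dropout rate, the required sample size is 14,975". The section then gives 15,586 as the number included, to allow for unqualified samples; sections 1.4 and 2.3 give 16,505.

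Section 2.3 sends subjects positive on miR-92a and/or FIT to colonoscopy. For the rest, section 6.6 says "a random sample of subjects who are negative for tests will be randomly selected for colonoscopy". Section 6.6.2 sets the number of sampled negatives to be comparable with the number of positives, in three draws (miR-92a-negative, FIT-negative, negative on both). Under section 8.1.3, negatives who are not drawn are not offered a free colonoscopy.

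Section 7.1.3 defines CRC sensitivity as the unweighted ratio a/(a + d). Section 7.4 adds: "Binomial proportions and exact 95% CI summarize sensitivity and specificity across categories".

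**The concern.** The step from 43 cancers to 14,228 subjects counts every cancer among evaluable subjects as found, including those the test misses. In this design a miR-92a-negative cancer is seen only if FIT is positive or the subject happens to be drawn. False negatives are few (about four expected) and carry most of the information about sensitivity, yet they are the cases left partly unverified. A reader of section 5.5 would expect CRC sensitivity to be estimated to within 9 points. The scheme gives either a less precise weighted estimate or an unweighted one that is too high.

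**Working it through.** **1. The plan's own figure.** Cancers needed: 1.96² × 0.9 × 0.1 / 0.09² = 42.68. Subjects: 42.68 / 0.003 = 14,228, as stated. With dropout: 14,228 / 0.95 = 14,977 against 14,975 stated, a trivial difference.

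**2. Expected counts in 14,228 evaluable subjects (section 5.5 rates).** CRC 42.7; AA 426.8; neither 13,758.5. miR-92a positives: 0.9 × 42.7 + 0.8 × 426.8 + 0.1 × 13,758.5 = 38.4 + 341.5 + 1,375.8 ≈ 1,756. Missed cancers: 42.7 − 38.4 = 4.3.

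**3. Assumptions not in the protocol.** FIT sensitivity 50-80% for CRC and 30% for AA; FIT false-positive rate 5-10%; FIT and miR-92a independent given disease status; every selected subject scoped. For FIT at 50% / 30% / 5%, the FIT-positives among miR-92a-negatives are 0.5 × 4.3 + 0.3 × 85.4 + 0.05 × 12,382.6 ≈ 647. That gives 2,403 positives on either test and 11,825 double negatives.

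Comparable number can be read as matching all positives (2,403 / 11,825 = 20.3% of double negatives drawn) or only the miR-92a positives (1,756 / 11,825 = 14.8%). Subjects scoped are then (2,403 + 2,403) / 14,228 = 33.8% or (2,403 + 1,756) / 14,228 = 29.2%.

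**4. Half-width for a weighted sensitivity.** Let Se = 0.9 and n = 42.68. Let q1 be the share of cancers missed by miR-92a but FIT-positive, q2 the share missed by both, and f the fraction of double negatives scoped. The large-sample half-width is

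1.96 × √{[(1 − Se)² Se + Se² (q1 + q2/f)] / n}.

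- Full verification (f = 1): (0.009 + 0.81 × 0.10) / 42.68 = 0.00211, half-width 0.090. The plan's figure is recovered; any f below 1 gives more.
- FIT CRC sensitivity 50%, f = 0.148: (0.009 + 0.81 × (0.05 + 0.05/0.148)) / 42.68 = 0.00757, half-width 0.170.
- FIT CRC sensitivity 80%, f = 0.270: (0.009 + 0.81 × (0.08 + 0.02/0.270)) / 42.68 = 0.00314, half-width 0.110.

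With so few false negatives the formula is slightly pessimistic, so I also simulated (400,000 runs per row; half-width taken as 1.96 × SD). The unweighted ratio is expected at about 0.9 / (0.9 + q1 + q2 f).

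| FIT CRC sens. | FIT false-pos. | Negatives matched to | f | Scoped | CRC half-width (simulated) | Unweighted CRC Se | No missed CRC seen | AN half-width |
|---|---|---|---|---|---|---|---|---|
| 50% | 5% | miR-92a positives | 0.148 | 29% | 0.157 | 0.940 | 9% | 0.073 |
| 50% | 5% | all positives | 0.203 | 34% | 0.143 | 0.937 | 8% | 0.063 |
| 50% | 10% | all positives | 0.270 | 42% | 0.130 | 0.934 | 7% | 0.056 |
| 80% | 5% | miR-92a positives | 0.148 | 29% | 0.121 | 0.916 | 3% | 0.072 |
| 80% | 10% | all positives | 0.270 | 42% | 0.108 | 0.913 | 3% | 0.056 |

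The three other combinations fall within these ranges.

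**5. Larger enrolment.** Even if all 16,505 were evaluable, the half-widths shrink only by √(14,228 / 16,505) = 0.93, to about 0.10-0.15.

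**6. Incomplete uptake.** With FIT CRC sensitivity 70% and false-positive rate 5%, the large-sample half-width is 0.129 at full uptake. It is 0.135, 0.144 and 0.160 if 80%, 60% or 40% of positives are scoped.

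**The case against.** Several counter-arguments have force.

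- **Most cancers are still verified.** This is true: about 41-42 of 42.7, because most are positive on one test. An interval computed on them looks about as narrow as planned, but it is centred too high. Weighting, which a statistical analysis plan not available here may specify, removes the bias but does not recover unseen false negatives, so the precision in section 5.5 is still not reached.
- **There is some protection in the plan.** Section 6.6.2 defers the random selection when a drawn negative refuses, apparently to another subject, and section 5.5 adds a margin above 14,975. Counting all three draws of negatives brings the half-width to roughly 10.5-14 points. None of this reaches 9 points, and it does not cover positives who decline.
- **The main objective is advanced neoplasia.** This stands. AN half-widths are 0.056-0.073 under the stated assumptions.
- **The 0.09 is a planning input.** This also stands. A reader might infer that the protocol reports CRC sensitivity as known to within 0.09; it makes no such claim.

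A reader might also infer a far worse case: a half-width of about 21 points, and about a 55% chance of seeing no missed cancer. Those figures follow if only miR-92a triggers colonoscopy and one equal-sized draw is made (f = 1,756 / 12,472 = 0.141). The protocol also scopes every FIT-positive, so they are a bounding case and do not describe this design.

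The exact intervals of section 7.4 differ from the Wald form used in planning. At 39/43 the exact interval is 77.9-97.4%, an average half-width of 9.8 points against 8.7. Planning one way and reporting the other is ordinary practice, and the point is minor.

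**Conclusion.** The point holds for CRC sensitivity. The number in section 5.5 is arithmetically right, but the precision attached to it belongs to a fully verified cohort of 14,228, and the protocol describes a partially verified one. The expected half-width of a weighted CRC sensitivity is about 11-16 points against 9 planned, and the unweighted ratio is about 1 to 4 points too high.

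The direction does not depend on the FIT assumptions: the half-width exceeds 0.09 whenever some double negatives go unscoped. The size does depend on them, and on the reading of comparable number and on full uptake.

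The documents do not support reading this as a failure of the whole trial or as a case for more enrolment. The AN target is expected to be met, even in the miR-92a-only bounding case (0.087).

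**What to change.** Do not enrol more. Revise section 5.5 as follows:

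- Say that 14,228 evaluable subjects give 0.09 for CRC sensitivity only under full verification.
- Give the expected precision of a sampling-weighted CRC sensitivity under the actual colonoscopy scheme: roughly 11-16 points, wider with incomplete uptake.
- Declare the FIT performance, the fraction of negatives sampled and the uptake behind that range. If the miR-92a-only figures are shown, label them as a bounding case.
- State that the 0.09 target is expected to be met for AN sensitivity, the main objective, and not for CRC sensitivity.

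The cost is protocol wording and a short simulation. The downside is a less favourable stated precision for CRC.

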6.1 Subjects enrolled

Subject enrolment will be initiated after the project has been approved by the ethical review committee. The researchers will determine whether to recruit subjects based on the inclusion and exclusion criteria, explain the study in detail to those who meet the enrolment criteria and are interested in participating in the trial, and answer all questions raised by the subjects to ensure that they are fully aware of the content of the study, the risks, benefits and other relevant information. The subject signs the informed consent to participate in the study. Subjects have the right to withdraw from the study at any stage after successful recruitment. Subjects may contact the study leader to inquire about test results or to request withdrawal.

The researcher will use the CRC risk questionnaire to interview the subjects after they have signed the informed consent to participate in the study. One copy of the informed consent will be retained by the subject after signing, and the other copy will be kept on file together with the subject's information and code. The subject code will be used as the unique identification number of the subject, which will be used to identify the samples, laboratory test data, and summarize the required information to meet the needs of information query and verification. Stool samples will be taken from the subjects.

11

6.2 Sample reception and storage

Generally, the FIT and miR-92a will be conducted on the same day. Researchers should mix the qualified fecal samples in the sample tubes within 12 h after receiving the samples, and then divide them into five 2 ml centrifuge tubes, each tube 0.3 - 0.5 g, and freeze them in a -80 °C refrigerator. If the sample cannot be packaged in a timely manner, the sample tube should be temporarily stored in a 4 °C refrigerator and the sample packaging and freezing should be completed within 24 h.

6.3 Fecal-based miR-92a test

One centrifuge tube of the subject's fecal samples will be used for fecal-based miR-92a testing, and the rest of the subject's fecal samples will continue to be frozen at -80 °C as a backup.

6.4 Fecal occult blood test

Allow the reagent chamber to stand at room temperature for 30 min before use. Open the foil pouch of FIT test, remove the colloidal gold test card and mark the sample number. Using a proctor, pick up the stool sample from multiple points (not less than 6 points) on the surface of the stool sample into the sample tube containing the diluent, mix well by inverting the sample, add 2-3 drops of liquid to the colloidal gold test card and observe the "C" and "T" lines within 5 min. FIT testing is completed immediately upon receipt of the sample.

6.5 Colonoscopy and/or pathology

Subjects are instructed to orally consume 3000 – 4000 ml of polyethylene glycol on the evening before the examination. During the examination, the endoscopist adheres to standardized protocols to ensure a comprehensive and clear visual of the anal canal, rectum, sigmoid colon, descending colon, transverse colon, ascending colon and ileocecal region. After microscopic lancing, clamping or scraping of the lesion, the tissue removed by the colonoscope is examined according to standard histopathological methods to determine the nature of the lesion.

6.6 Follow-up management

According to the protocol design and workflow, the study will be conducted in subjects who are positive for fecal-based miR-92a and/or FIT, and a random sample of subjects who are negative for tests will be randomly selected for colonoscopy, and subjects will be followed up until completion of colonoscopy. Individuals who have undergone

screening and require confirmatory testing should promptly schedule a colonoscopy and engage in health education sessions without delay.

6.6.1 Subjects tested positive for fecal samples

The researchers actively followed up with positive subjects, i.e., fecal miR-92a positive subjects, FIT positive subjects, miR-92a + FIT positive subjects, and provided education on bowel health and CRC prevention while facilitating the timely completion of colonoscopy.

The researchers counted the results of fecal samples in batches and contacted the subjects with positive fecal miR-92a and/or FIT tests to follow up with them to receive the colonoscopy and to make an appointment for the colonoscopy. After confirming the subject's acceptance of the colonoscopy and setting a date for the colonoscopy, the researcher contacted the subject again to follow up with him/her to learn about the colonoscopy precautions and to remind him/her to pick up the medications and materials needed for the bowel preparation. The researcher retrieved the colonoscopy report and pathology results in a timely manner after the subject completed the colonoscopy.

6.6.2 Subjects tested negative for fecal samples

The researchers actively followed up with randomly selected subjects under the following three conditions and provided education on bowel health and bowel cancer prevention while promoting timely completion of colonoscopies:

- A comparable number of fecal miR-92a-positive subjects were randomly chosen from among the fecal miR-92a-negative subjects.
- A comparable number of FIT-positive subjects were randomly chosen from among the FIT-negative subjects.
- A comparable number of fecal miR-92a & FIT-positive subjects were randomly chosen from among the fecal miR-92a & FIT-negative subjects.

Random method: Develop a Microsoft Excel worksheet to systematically categorize and enumerate all fecal test-negative subjects who have successfully undergone fecal sample testing but have not been randomized. Specifically, segregate the subjects into three distinct groups: those who tested negative for fecal miR-92a, those who tested negative for FIT, and those who tested negative for both fecal miR-92a and FIT. Number each subject within their respective group, and categorize them further based on age groups, with a distinct consideration for gender. Populate column A with the sequential subject numbers for each age-gender group. Utilize the Random function in column B, executing the command by pressing the Enter key, and subsequently generate the data columns by dragging down the cells. Select the

corresponding subject numbers for follow-up in ascending order to ensure a systematic and unbiased approach for further analysis.

Random example: A cohort of 200 subjects, who had undergone stool sample testing but had not been randomized, comprised the study population. This group included 120 males and 80 females. Notably, within the 51 – 55 age bracket of male subjects, 40 individuals were evaluated, among whom 3 tested positives for miR-92a. Subsequently, the researchers adopted a randomized approach to select 3 of the remaining 37 male subjects within this age group, who had negative miR-92a test results, for active follow-up and colonoscopy. The methodology employed for this selection and subsequent colonoscopy procedure is outlined below.

- Create a new Microsoft Excel worksheet and enter the subject numbers of fecal miR-92a test-negative male subjects in the 51-55 age group in column A, e.g., SZH00051-SZH00087.
- In cell B1 enter the function: = RAND ().
- After clicking on the model to execute the function, drop down the cell and generate random data.
- Select the data cells in column B, right-click the mouse and select "Sort" in the "ascending".
- By expanding the selected region, the data in column A can be redistributed randomly.
- Select the first three rows of the worksheet, select the toolbar in the "data" menu in the "combination" option, read
 the number obtained that is randomly selected subjects.
- Initiate a follow-up telephone call with three randomly selected subjects to follow up on the completion of the colonoscopy. If any of the subjects refused to undergo colonoscopy, the randomized follow-up subjects were deferred.

6.7 Information entry and collation

Information including CRC risk questionnaire, subject code, age, gender, fecal-based miR-92a test results, FIT test results, colonoscopy and pathology results, and hospital discharge diagnosis or medical records will be aggregated by the investigator into the research database after removing personally identifiable information. Subject enrolment, sample testing and compilation of information will be conducted simultaneously to allow the investigator to provide timely feedback on subsequent enrolment based on sample collection and testing. Personal identification information includes, but is not limited to, the subject's name, ID card number, social security account number, driver's license number, clinic number, hospitalization number and any other information that can directly or indirectly identify the subject.

6.8 Research materials and equipment

The company provides stool sample collection kits, nucleic acid extraction reagents, fecal-based miR-92a test reagents, FIT test reagents, and any other materials necessary for the collection of stool samples from subjects and for laboratory testing. Clinical facilities conducting the trial will provide space, equipment and materials for colonoscopy and histopathology examinations.

6.9 Back-up sample storage

Backup samples will be kept in a refrigerator at -80 °C in the clinical medical research center for future traceability and verification, and the samples will be kept for no more than 2 years.

7. Data analysis

7.1 Test termination points

7.1.1 Relevant definitions

The main objective of the study was to examine the performance of FIT, miR-92a, and FIT + miR-92a for AN. Colonoscopy and histopathology were used as the gold standard to determine the classification of the subject.

Sayooning toot	Colonoscopy and histopathology		
Screening test	Patients	Nonpatients	
Positive	True positive (TP)	False positive (FP)	
Negative	False negative (FN)	True negative (TN)	

When counting the performance of different screening protocols for CRC, subjects with a positive screening test result and a confirmed colonoscopy diagnosis of CRC were counted as true positives, otherwise they were counted as false positives, and subjects with a negative screening test and a confirmed colonoscopy diagnosis of a non-colorectal cancerous lesion, such as a normal, inflamed, polyps, advanced adenoma, or other non-colorectal cancerous lesion were counted as true negatives, otherwise they were counted as false negatives.

When counting the performance of different screening protocols for AN (CRC and AA), a positive screening test with a confirmed colonoscopy diagnosis of CRC or AA was counted as a true positive, otherwise it was counted as a

false positive, and a negative screening test with a confirmed colonoscopy diagnosis of a normal, inflamed, polyps, or other non-colorectal cancerous lesion was counted as a true negative, otherwise it was counted as a false negative.

Specific screening and analysis performance indicators are calculated as follows:

- Sensitivity (SN): also known as true positive rate (TPR), defined as true positive/ (true positive + false negative) × 100%;
- Specificity (SP): also known as true negative rate (TNR), defined as true negative/ (true negative + false positive) × 100%;
- Accuracy (ACC): defined as (true positive + true negative)/ (positive + negative) × 100%;
- Positive predictive value (PPV): defined as true positive/ (true positive + false positive) × 100%;
- Negative predictive value (NPV): defined as true negative/ (true negative + false negative) ×100%.

7.1.2 Categorization of participants based on colonoscopy and histopathology

Colonoscopy and/or histopathological findings were classified as AA if they met any of the following criteria:

- Colonoscopy and/or pathology for carcinoma in situ;
- Serrated polyps with maximum size ≥ 1 cm on colonoscopy and/or pathology;
- Tubular/chromosomal adenoma (≥ 25% choriocapillaris) of any size on colonoscopy and/or pathology;
- Tubular adenoma with high-grade intraepithelial neoplasia of any size on colonoscopy and/or pathology;
- Tubular adenoma, low-grade intraepithelial neoplasia, maximum size ≥ 1 cm on colonoscopy and/or pathology;
- A colonoscopy and/or pathology that did not meet any of the above criteria and did not meet the criteria for cancer
 was classified as normal or polyp or other, as determined by the colonoscopy and/or pathology.

Colonoscopy and histopathological findings of cancer will be staged according to TNM staging criteria as follows:

		Т	N	M
0	0	Tis	N0	M0
I	I	T1/T2	N0	M0
II	II	T3/T4	N0	M0
	IIA	Т3	N0	M0
	IIB	T4a	N0	M0
	IIC	T4b	N0	M0
III	III	Tis-T4	N+	M0
	IIIA	T1 – T2	N1	M0
		T1	N2a	M0
	IIIB	T3 – T4a	N1	M0
		T2	N2a	M0
		T1-T2	N2b	M0
	IIIC	T4a	N2a	M0
		T3 – T4a	N2b	M0
		T4b	N1 - N2	M0
IV	IV	Tis-T4	N0 - N2	M+
	IVA	Tis-T4	N0 - N2	M1a
	IVB	Tis-T4	N0 - N2	M1b

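### The third advanced-adenoma criterion in section 7.1.2 cannot be applied as printed, so villous lesions have no clear place in the definition of the main target

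*Protocol*

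**What the plan says.** Section 7.1.2 opens with the rule "Colonoscopy and/or histopathological findings were classified as AA if they met any of the following criteria". Five findings follow:

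- first, carcinoma in situ;
- second, a serrated polyp that reaches 1 cm;
- third, the line at issue here, which reads "Tubular/chromosomal adenoma (≥ 25% choriocapillaris) of any size on colonoscopy and/or pathology";
- fourth, high-grade neoplasia whatever the size, but only in a tubular adenoma;
- fifth, the size rule for low-grade lesions, again confined to one histology: "Tubular adenoma, low-grade intraepithelial neoplasia, maximum size ≥ 1 cm on colonoscopy and/or pathology".

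The closing bullet takes "A colonoscopy and/or pathology that did not meet any of the above criteria and did not meet the criteria for cancer" and says that it "was classified as normal or polyp or other, as determined by the colonoscopy and/or pathology". The frequency table in section 7.1.3 puts polyps and other non-cancerous lesions in the NEG column.

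On the source of the diagnosis, section 7.1.1 states: "Colonoscopy and histopathology were used as the gold standard to determine the classification of the subject". Section 7.2 also joins the two with *and*. Sections 1.3 and 2.3, the table in 7.1.3 and the criteria in 7.1.2 use *and/or*.

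**The concern.** Section 7.1.2 is the outcome definition: it decides who counts as diseased. Its third line names a type of adenoma that does not exist and sets a 25% threshold on a tissue of the eye. The line appears to be meant for adenomas with a villous component, but the word villous occurs nowhere in the protocol, so a reader has to guess.

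Two readings are possible, and they err in opposite directions. A literal reader finds no line for villous histology and sends the lesion to NEG, even at 2 cm. A reader who ignores the parenthesis is left with a tubular adenoma of any size, which admits every tubular adenoma and makes the high-grade and 1 cm criteria redundant. Section 2.3 names three hospitals, and they could class the same lesion differently.

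AN is the main target and AA supplies most of it. A test-positive lesion wrongly sent to NEG turns a true positive into a false positive, and a test-negative one turns a false negative into a true negative.

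**Working it through.** **Where a villous adenoma goes under each line, read literally**

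| Line in 7.1.2 | Does a villous or tubulovillous adenoma qualify? |
|---|---|
| Carcinoma in situ | Only if reported as such |
| Serrated polyp, at least 1 cm | No, different histology |
| Third criterion | No, the terms match no bowel lesion |
| High-grade neoplasia | No, tubular adenoma only |
| Low-grade, at least 1 cm | No, tubular adenoma only |
| Residual bullet | Yes, hence NEG in 7.1.3 |

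**Inputs from section 5.5.** CRC prevalence 0.3%, AA prevalence 3%; sensitivity 90% for CRC and 80% for AA; specificity 90%; allowable error W = 0.09.

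**The plan's own figures.** N1 = 1.96² × SN(1 − SN) / W² / P.

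- AA: 3.8416 × 0.16 / 0.0081 = 75.88; 75.88 / 0.03 = 2,529, as stated.
- CRC: 3.8416 × 0.09 / 0.0081 = 42.68; 42.68 / 0.003 = 14,228, as stated.

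These rest on assumed prevalences and do not change with the histological wording.

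**Baseline at N = 14,228**

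- CRC = 42.7, AA = 426.8, AN = 469.5, NEG = 13,758.5.
- AA share of AN = 300 / (300 + 30) = 91%.
- Test-positives = 0.9 × 42.7 + 0.8 × 426.8 + 0.1 × 13,758.5 = 38.4 + 341.5 + 1,375.8 = 1,755.7.
- PPV(AN) = (38.4 + 341.5) / 1,755.7 = 21.6%.
- Sensitivity for AN = 379.9 / 469.5 = 80.9%.

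**Effect of the literal reading.** Let v be the share of AA that qualifies only by the third line. The protocol gives no value, so 10% to 30% is an assumption. The moved lesions are taken to be test-positive at the same 80%.

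- PPV(AN) = (379.9 − 0.8 × v × 426.8) / 1,755.7
- Specificity = 1 − (1,375.8 + 0.8 × v × 426.8) / (13,758.5 + v × 426.8)
- Sensitivity(AN) = (379.9 − 0.8 × v × 426.8) / (469.5 − v × 426.8)

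| v | AA moved to NEG | of these test-positive | PPV(AN) | Specificity | Sensitivity(AN) |
|---|---|---|---|---|---|
| 0 | 0 | 0 | 21.6% | 90.0% | 80.9% |
| 10% | 43 | 34 | 19.7% | 89.8% | 81.0% |
| 20% | 85 | 68 | 17.7% | 89.6% | 81.1% |
| 30% | 128 | 102 | 15.8% | 89.4% | 81.3% |

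If the moved lesions were detected at a different rate, sensitivity would shift. With v = 10%, AA sensitivity would be (0.8 − 0.1 × 0.6) / 0.9 = 82.2% if they were detected at 60%, and (0.8 − 0.1 × 0.95) / 0.9 = 78.3% if at 95%.

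**Verification.** The table treats every subject as verified. Section 2.3 sends all test-positives to colonoscopy but only a random selection of test-negatives. The PPV column therefore needs only that positives complete colonoscopy; the specificity and sensitivity columns are illustrative.

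**The opposite reading.** Admitting all tubular adenomas would enlarge AA. The protocol gives no frequency for small low-grade tubular adenomas, so this cannot be sized.

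**The case against.** The best defence is that nobody would apply the line literally. The English is rough throughout: section 4.3.4 equates two drops with 80 ml, and section 5.4 garbles the wording on how far the colonoscope must reach. The 25% threshold and the paired adenoma terms let a specialist guess the intent, and hospital pathologists may well have coded lesions as intended. This stands as far as it goes. It makes a miscount less likely, but an outcome definition should not depend on a guess.

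A reader might infer three stronger points that the documents do not support.

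- **That the AA and AN counts are wrong.** The protocol holds no counts, and nothing shows how any lesion was coded. Nor is the third line the only route to AA for a villous lesion, since carcinoma in situ is not limited to tubular adenoma.
- **That endoscopy alone can create an AA case.** The criteria ask for histological labels. Sections 4.4 and 6.5 send removed tissue to histopathology, and section 8.1.3 has lesions sampled when found. What remains is a conflict of wording between *and/or* and *and*.
- **That letting either size reading meet the 1 cm threshold is an error.** The rule is determinate and cuts both ways. With two independent readings of SD 1.5 mm (assumed), a true 9 mm adenoma reaches 10 mm with probability 25% on one reading and 44% on either; a true 11 mm adenoma is missed 25% of the time on one and 6% on either. Preferring one size source is a matter of choice.

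**Conclusion.** The point holds as a defect in the outcome definition. The third AA criterion cannot be applied as printed. No other line clearly catches a villous or tubulovillous adenoma unless it is reported as carcinoma in situ, and the residual bullet then counts it as negative. Misclassification is possible in either direction; none is demonstrated.

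On a literal reading the cost falls mainly on PPV(AN), with a loss of about 2 to 6 percentage points. Specificity loses at most about 0.6 points and AN sensitivity barely moves. These sizes rest on the planning values in section 5.5, an assumed 10% to 30% share of AA that qualifies only by this line, equal detection at 80%, and full verification for specificity and sensitivity. That the line means a villous component is itself an inference, though a strong one. The sample size is not affected.

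**What to change.** 1. Restate the third criterion as what it appears to intend: villous or tubulovillous adenoma, at least 25% villous component, any size. Because the protocol never uses the word villous, confirm this against the source-language protocol, if the English text is a translation.
2. Check against the stored pathology reports that lesions with a villous component were coded as AA at all three hospitals, and that small low-grade tubular adenomas were not. Recode any that were not handled this way, and report how many changed.
3. Reconcile *and/or* in section 7.1.2 with *colonoscopy and histopathology* in sections 7.1.1 and 7.2, so that an AA or CRC classification rests on histology. *And/or* can be kept for examinations in which there was nothing to sample.

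The cost is a change of wording and a review of existing reports; no new procedure is needed. One consequence to accept is that a lesion seen but never sampled cannot count as AA.
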